10.12. Appendix 12: Protocol Amendment History

The Protocol Amendment Summary of Changes Table for the current amendment is located directly before the Table of Contents (TOC).

Amendment 2 (2 December 2022)

Overall Rationale for the Amendment: The main purpose of this amendment is to implement regulatory feedback with regards to study pausing in case of safety concerns. In addition, it was clarified that participants with certain laboratory abnormalities at baseline (Day 1) will be discontinued from study intervention. Serum lipase was added to the blood chemistry panel and a clarification concerning the recording of body temperature was added.

The changes made to the clinical protocol 64281802DNG2004 as part of Protocol Amendment 2 are listed below, including the rationale of each change and a list of all applicable sections.

Section number	Description of Change	Brief Rationale
and Name	2 to trapion of change	2131144101441
7.1.2 Study Pausing Criteria;	Study pausing criteria were added.	Upon Health Authority request
8.3.1 Time Period and	The sponsor's medical monitor (or	
Frequency for Collecting	designee) will do a thorough analysis of	
Adverse Event and Serious	all reported ≥Grade 3 unsolicited AEs to	
Adverse Event Information;	determine whether a safety data review by	
10.6.6 Committees Structure	the IDMC is warranted. If the IDMC	
	judges that the study pausing criteria have	
	been met, the IDMC will recommend to	
	either pause the study or to implement	
	modifications to the study conduct and/or	
	to the safety assessments.	
	In addition, it was clarified that the	
	investigator should notify the sponsor's	
	medical monitor (or designee)	
	immediately and no later than 24 hours	
	after becoming aware of any ≥Grade 3	
	unsolicited AE considered related to study	
	intervention.	
7.1 Discontinuation of Study	It was clarified that participants who	To ensure that participants with
Intervention	report with 2 or more ≥Grade 2 laboratory	clinically significant laboratory
	abnormalities for elevations of	abnormalities at baseline
	triglycerides, low-density lipoprotein	discontinue treatment with study
	cholesterol, and/or total cholesterol,	intervention.
	and/or 2 or more ≥Grade 2 laboratory	
	abnormalities for other laboratory	
	parameters at baseline (Day 1) will be	
10.0 A 1:- 0. Clinia -1	discontinued from study intervention. Serum lipase will be monitored during the	Upon Health Authority request
10.8 Appendix 8: Clinical Laboratory Tests	dosing and follow-up phases.	Opon Health Authority request
1.3.2.2 Double-blind	It was clarified that body temperature will	Clarification
Prophylactic Dosing: Day 1	be recorded by the participant in a diary	Ciarmeation
to Day 13;	daily (preferably at the same time each	
1.3.2.3 Double-blind	day) and in case of feeling feverish, and	
Prophylactic Dosing (Day 14	that it will be added to the CRF by study	
to Day 28) and Follow-up	site personnel only in case the body	
Phase;	temperature is \geq 37.5°C (99.5°F).	
8 STUDY ASSESSMENTS	(7).3 1).	
AND PROCEDURES;		
THE TROCLDORES,		

Section number and Name	Description of Change	Brief Rationale
8.2.2 Vital Signs		
Throughout the protocol	Minor grammatical, formatting, or spelling changes and clarifications were made.	Minor errors were corrected.

Amendment 1 (04 October 2022)

Overall Rationale for the Amendment: The main purpose of this amendment is to remove serology as a criterion for identifying dengue virus (DENV) infection in household contacts (HHC) for the evaluation of the prophylactic effect of JNJ-64281802 for the primary endpoint. In addition, the measurement of anti-DENV antibodies was moved from a secondary to an exploratory endpoint. Other changes in this amendment include the following:

- The diagnosis of DENV infection in index cases was clarified, and the possibility of using anti-DENV IgM test if necessary was added.
- The follow-up period was extended to 62 days following the last dose.
- The calculation of the prophylactic efficacy was adjusted.
- The requirement to have energy bars along with the study intervention was removed.
- The other changes, such as performing clinical laboratory analyses in local laboratories, were made for logistical reasons.

Section number	Description of Change	Brief Rationale
and Name		
1.1 Synopsis: Hypothesis; primary endpoint; 9.1 Statistical Hypotheses; 9.4.2 Primary Endpoint(s)	 Removed serology as a criterion for identifying laboratory-confirmed DENV infection in HHC. Specified the definition of laboratory-confirmed DENV infection. 	- To restrict the identification of lab-confirmed DENV infection to detection of the DENV virus itself (either viral RNA and/or NS1 antigen) as detection of anti-DENV antibodies can be hampered by many variable factors such as cross reactivity with other flaviviruses To clarify what is meant by laboratory-confirmed DENV infection.
1.1 Synopsis: Objectives and Endpoints; Statistical Methods; 3 OBJECTIVES AND ENDPOINTS	Measurement of anti-DENV antibodies was moved from a secondary objective to an exploratory objective.	As the detection of anti-DENV antibodies can be hampered by many variable factors, this analysis was moved to exploratory objective.
1.1 Synopsis: Objectives and Endpoints; 3 OBJECTIVES AND ENDPOINTS	Removal of the analysis of neutralizing antibodies as an exploratory objective. It will be analyzed in an exploratory research.	Detection of neutralizing antibodies can be hampered by many variables.
1.1 Synopsis; 1.3.1 Index Cases; 4.1 Overall Design; 5.1 Inclusion Criteria 8.7.1 NS1 Rapid Test and RT-PCR of Index Cases	The criteria for identifying index cases were modified to include the possibility of using anti-DENV IgM test.	To allow for the possibility to use an alternative anti-DENV IgM test when a DENV NS1 or DENV PCR test is not available.
1.3.2.2 Double-blind Prophylactic Dosing: Day 1 to Day 13; 1.3.2.3 Double-blind Prophylactic Dosing (Day 14 to Day 28) and Follow-up Phase	Blood samples should be taken prior to the first drug intake only on Day 1.	Day 1 predose blood sample required as baseline sample, other sampling points can be done at any time points of the visit day to facilitate operational conduct of the trial.

Section number	Description of Change	Brief Rationale
and Name 1.1 Synopsis: Overall Design - Follow-up Phase; 1.3.2.3 Double-blind Prophylactic Dosing (Day 14 to Day 28) and Follow-up Phase; 4.1 Overall Design Follow- up Phase; 4.4 End of Study Definition Study Completion Definition; 8 STUDY ASSESSMENTS AND PROCEDURES	- A follow-up visit and immune assessments on Day 90, and phone follow-ups between Day 50 and Day 90 were added The approximate duration of the study was changed from 7 weeks to 13 weeks to reflect the additional follow-up Clarified in footnote that concomitant medications and AEs will be reviewed throughout the follow-up period until Day 90.	To assess post-treatment DENV serology and to document and review any cases of symptomatic dengue during an extended follow-up period.
1.3.2.3 Double-blind Prophylactic Dosing (Day 14 to Day 28) and Follow-up Phase	 Specified that participants showing signs or symptoms of DENV infection between Day 28 and Day 90 had to come to the study site. Specified that after Day 28 the occurrence of AEs will be based on phone monitoring in addition to the site visits on Days 40, 50, and 90. Added a window of +/- 1 day to the Day 28 visit. 	 To ensure that blood would be drawn for antiviral activity assessment and viral sequencing for infections that occur after the last dose. To ensure safety is regularly monitored between participants' site visits. To allow for the Day 28 blood sampling to occur on a Monday in case Day 28 is a Sunday.
1.2 Schema Figure 1: Schematic Overview of the Study	The number of days between the end of treatment and follow-up was modified.	To account for the additional Day 90 follow-up.
1.1 Synopsis: Description of Intervention; 1.3.2.2 Double-blind Prophylactic Dosing: Day 1 to Day 13; 4.3 Justification for Dose 6.1 Study Intervention(s) Administered; Table 2; 8 STUDY ASSESSMENTS AND PROCEDURES	The requirement to have an energy bar was removed.	The impact of additional energy on bioavailability was minimal based on data from the relative bioavailability study 64281802DNG1006.
2.2 Background	An additional result from Part 2 of study 64281802DNG1006 was added.	To explain why energy bars were no longer required with dosing.
6.8 Concomitant Therapy	 Domperidone was removed from the list of concomitant medications that are not allowed. Concomitant medications that are prohibited were updated. 	Newly collected information on JNJ-64281802 as an inhibitor and inducer of various CYP enzymes and transporter proteins obtained in Study DNG1005 has led to the revision of disallowed concomitant medication.
2.2 Background; 2.3.1 Risks for Study Participation	Summary of study 64281802DNG1004 was added. The safe doses were updated based on study 64281802DNG1004.	For completeness since the final 64281802DNG1004study report became available.
2.2 Background Study DNG1001	In the Background section, the safety summary of Study 64281802DNG1001 was modified for consistency with the text in other documents.	For consistency with other Phase 2 protocols and the Investigator's Brochure.

Section number and Name	Description of Change	Brief Rationale	
1.3.2.3 Double-blind Prophylactic Dosing (Day 14 to Day 28) and Follow-up Phase	An additional pregnancy test was added on Day 28.	To increase the likelihood of detecting a pregnancy while on the study intervention.	
1.1 Synopsis: Statistical Methods; 9.4.4.1 Safety Analyses 10.2 Appendix 2: Rash Management	Rash was added as an event that requires narrative reporting. Clarified that rashes are to be assessed by investigators at their discretion. All rashes that are not related to DENV infection are to undergo rash management assessment.	To generate more comprehensive clinical data and better assess rashes that are not related to dengue infection.	
1.1 Synopsis: Statistical Methods; 9.4.2 Primary Endpoint(s)	- Clarified the calculation of prophylactic efficacy: The odds-ratio from the logistic regression model will be used to estimate prophylactic efficacy The statement referring to interim analysis in the sensitivity analysis was deleted.	 Given the expected low incidence, the odds ratio will be a very good approximation of the relative risk. The reference to the Interim Analysis section is not needed as no sensitivity estimators are planned for the interim analysis. 	
1.1 Synopsis: Statistical Methods; 4.1 Overall Design; 9.2 Sample Size Determination	The number of participants expected to be enrolled was updated from 1,300–1,850 to 1,250–1,850.	The number of expected participants was recalculated.	
10.6.8 Data Quality Assurance; 10.8 Appendix 8: Clinical Laboratory Tests	- Clarification made that hematology and microscopic urinalysis must be performed by local laboratories and results entered by the clinical site staff Lactose dehydrogenase (LDH) and bicarbonate were removed from the list of analytes for clinical chemistry.	- For protocols performed in remote settings, sample shipment times can exceed the specimen viability time, and central laboratory analysis cannot be performed due to sample degradation. This directly impacts monitoring of participant safety. Therefore, for perishable samples, hematology testing and microscopic urinalysis will be performed locally. - Analysis of LDH and bicarbonate were not deemed medically necessary for the analysis and assessment of safety for this study.	
8 STUDY ASSESSMENTS AND PROCEDURES Overview; 10.8 Appendix 8: Clinical Laboratory Tests	Alcohol test was kept general and not limited to a breath test.	Some study sites do not use alcohol breath test.	
1.1 Synopsis: Number of participants; 5.1 Inclusion Criteria	The maximum body mass index in the inclusion criteria was increased from 33 to 35.	To reduce screen failures due to BMI. No implications for safety are expected.	

Section number and Name	Description of Change	Brief Rationale
2.3.1 Risks for Study Participation; 5.2 Exclusion Criteria; 6.8 Concomitant Therapy 10.4 Appendix 4: COVID 19 Appendix	 The vaccination exclusion criterion was modified so that it excluded attenuated COVID-19 vaccination. Clarification regarding COVID-19 vaccinations in the exclusion criteria. 	- To allow for vaccination against COVID-19. - Attenuated COVID-19 vaccines and boosters (if these become available during the study) were included in the exclusion criteria since information on the type of vaccine (live or non-live attenuated) taken may not be readily available. Once the study intervention has stopped, receiving COVID-19 vaccination is up to the discretion of the investigator.
1.1 Synopsis: Objectives and Endpoints; 3 OBJECTIVES AND ENDPOINTS	Modification of the exploratory endpoints.	The exploratory endpoints were phrased more precisely.
1.1 Synopsis: Objectives and Endpoints; 3 OBJECTIVES AND ENDPOINTS	Removal of the exploratory objective to evaluate the prophylactic effect of JNJ-64281802 with respect to the prevention of laboratory-confirmed DENV infection up to Day 50 among HHC who have no evidence of current DENV infection at baseline and who completed study intervention.	Laboratory-confirmed DENV infection is defined as a positive result on the DENV RNA and/or DENV NS1 protein assay. In order not to miss the detection of a laboratory-confirmed DENV infection, at least twice weekly sampling is necessary, which is only planned up to Day 28.
1.1 Synopsis: Description of Study Intervention; Table 2	CCI	CCI
1.3.2.4 Discontinuation From Study Intervention or Study; 7.1 Discontinuation of Study Intervention	Addition that immune assessments, viral analysis, and viral sequencing will be performed at withdrawal and follow-up visits when participant discontinues from the study or study intervention.	Sequencing at these time point added (consistent with other sampling time points) to characterize DENV variants associated with resistance to JNJ-64281802.
1.3.2.4 Discontinuation From Study Intervention or Study	 Clarified that upon the visit at discontinuation, participants will come to the study site. Added footnote (d) Modified the description of the follow-up visit (removed "Safety" and made clarifications in footnote d) 	- Since ECG measurements will have to be taken, the withdrawal visit needs to be at the study site To specify that safety assessments and clinical laboratory tests at follow-up will be performed at the discretion of investigators To clarify that the follow-up visit is performed mainly for antiviral and immune assessments. No safety issues are expected.

Section number	Description of Change	Brief Rationale
and Name		
1.3.2.5 Pharmacokinetic Substudy; 6.4 Study Intervention Compliance; 8 STUDY ASSESSMENTS AND PROCEDURES Sample Collection and Handling	 Requirement for study site visit on Days 29 and 32 in the PK Substudy was made optional. The requirement to visit study site on Days 2 and 3 was specified in the footnote. 	Visit can be performed at the site or at home.To maintain consistency with the table.
7.2.1 Withdrawal From the Use of Research Samples	Clarified that the only optional research samples are for pharmacogenomics.	To clarify that the only optional samples are for pharmacogenomics.
1.1 Synopsis: Safety Analysis 1.3.2.2 Double-blind Prophylactic Dosing: Day 1 to Day 13; 1.3.2.3 Double-blind Prophylactic Dosing (Day 14 to Day 28) and Follow-up Phase; 8 STUDY ASSESSMENTS AND PROCEDURES 8.2.2 Vital Signs	Removed body temperature from vital signs. Specified that body temperature needs to be recorded only in case of fever.	To clarify that normal body temperature does not need to be recorded.
5.2 Exclusion Criteria	Removed the specification that constipation is considered as an exclusion criterion if it lasts >2 days.	To consider any occurrence of constipation as an exclusion criterion.
6.7 Treatment of Overdose	The option for the decision to be taken in case of overdose was changed to continue (or discontinue) study intervention.	No study treatment interruption or modification is allowed in the study.
Throughout the protocol	Minor grammatical, formatting, or spelling changes and clarifications were made.	Minor errors were corrected, and clarifications added.

1. INTRODUCTION

This statistical analysis plan (SAP) contains definitions of analysis sets, derived variables and statistical methods for the analysis of efficacy and safety of study drug JNJ-64281802. A separate document, the data presentation specifications (DPS), for mock shells and a table of contents for tables, figures and listings is also produced. The SAP is to be interpreted in conjunction with the protocol¹ (amendment 3).

The study was prematurely ended on 02 October 2024 when 21 laboratory confirmed dengue infections between baseline and last day of dosing (+1 day) were observed in the primary analysis population and 14 symptomatic dengue infection between baseline and last day of dosing (+1 day) were observed in the complete study population. This decision was taken by Johnson & Johnson based on portfolio reprioritization and was not based on any safety concerns. The current SAP will cover the final analysis (FA). Changes to the per protocol planned analysis are described in section 6.2, Appendix 2.

1.1. Objectives and Endpoints

The primary, secondary and exploratory objectives and endpoints covered in this SAP are listed below.

	Objectives	Endpoints		
Pri	mary			
•	To evaluate the prophylactic effect of JNJ-64281802 with respect to the prevention of laboratory-confirmed DENV infection among household contacts (HHCs) who have no evidence of current DENV infection at baseline.	•	Laboratory-confirmed DENV infection ^a between baseline and the last day of dosing + 1 day.	
Ke	y Secondary			
•	To evaluate the prophylactic effect of JNJ-64281802 with respect to the prevention of symptomatic DENV infection through development of signs and symptoms (see Safety Evaluations section) among all HHCs.	•	Laboratory-confirmed symptomatic DENV infection ^b between baseline and the last day of dosing + 1 day.	
Sec	ondary			
•	To evaluate the prophylactic effect of JNJ-64281802 with respect to the prevention of symptomatic DENV infection through development of signs and symptoms (see Safety Evaluations section) among HHCs who have no evidence of current DENV infection at baseline.	•	Laboratory-confirmed symptomatic DENV infection ^b between baseline and the last day of dosing + 1 day.	
•	To assess the safety and tolerability of 2 dose regimens (high and low) of JNJ-64281802 among HHCs.	•	Safety and tolerability as measured by recording of adverse events (AEs), serious adverse events (SAEs), physical examinations, vital signs, electrocardiograms (ECGs), and clinical laboratory assessments.	

CONFIDENTIAL – FOIA Exemptions Apply in U.S.

Objectives	Endpoints		
To assess the pharmacokinetics (PK) of JNJ-64281802 following repeated oral dosing among HHCs.	Observed analyte concentrations over time.		
Exploratory			
To evaluate the prophylactic effect of JNJ-64281802 with respect to the prevention of DENV infection as measured through increase of anti-DENV antibodies among HHCs who have no evidence of current DENV infection at baseline.	 Increase in anti-DENV antibodies between baseline and Day 40. Increase in anti-DENV antibodies between baseline and Day 50. Increase in anti-DENV antibodies between baseline and Day 90. 		
To identify circulating DENV serotypes/genotypes and genetic variants among index cases and HHCs.	 Serotype/genotype of DENV based on viral genome sequence analysis. Genetic variation of viral genome sequence based on changes at the amino acid level. Emergent JNJ-64281802 resistance-associated mutations in HCC using index case sequence as reference. 		

AE = adverse event; DENV = dengue virus; ECG = electrocardiogram; HHC=household contact; RNA=ribonucleic acid; NS = non-structural protein; PCR = polymerase chain reaction; SAE = serious adverse event.

- ^a DENV infection is defined as a positive DENV RNA or DENV NS1 protein test result.
- Laboratory-confirmed symptomatic DENV infection is defined as having at least 2 solicited systemic AEs (see Safety Evaluations section), of which at least one is a most common dengue symptom (ie, fever, headache/retro-orbital pain, myalgia, arthralgia, rash), lasting for ≥1 day and occurring within a +/-2 days time window around the positive PCR or NS1 test.

The statistical analysis for the following exploratory objectives might be performed, but will depend on the unblinded results of the primary and secondary endpoints, for hypothesis generating purposes:

Objectives	Endpoints
Exploratory	
To evaluate the prophylactic effect of JNJ-64281802 with respect to reduction of DENV RNA among enrolled HHCs who have no evidence of current DENV infection at baseline and who are infected post baseline.	• The maximum DENV RNA levels between baseline and the last day of dosing + 1 day.
To evaluate the antiviral effect of JNJ-64281802 as early treatment among HHCs who have evidence of DENV infection at baseline.	 Time to end of detectable DENV RNA and/or reduction in DENV RNA load. DENV-associated signs and symptoms.

HYPOTHESIS

See Section 2, Statistical Hypotheses.

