9.3. Populations for Analysis Sets

For purposes of analysis, the following populations are defined:

Population	Description		
Enrolled	All participants (index cases and HHCs) who signed the ICF.		
Index Case	All participants enrolled as an index case, with a laboratory-confirmed DENV infection.		
population			
Randomized	All participants (HHCs) who are randomized in the study.		
Safety	All randomized participants who received at least one dose of study intervention.		
	This population will be used for the safety analysis.		
Primary study population	All randomized participants who received at least one dose of study intervention and who ha no evidence of current DENV infection (based on negative results for DENV RNA and NS1 protein assays) at baseline.		
	This population will be used for the primary, secondary, and exploratory efficacy analyses.		
Secondary study population All randomized participants who received at least one dose of study intervent evidence of current DENV infection (based on positive results for DENV RN protein assays) but without DENV signs and symptoms at baseline.			
	This population will be used to evaluate the exploratory objective of an antiviral effect of JNJ-64281802 as early treatment.		
Complete study	All randomized participants who received at least one dose of study intervention and without		
population	DENV signs and symptoms at baseline.		
	This population will be used to investigate the key secondary endpoint of the effect of JNJ-64281802 on the prevention of symptomatic DENV infection.		
PK	All participants who received at least one dose of study intervention and who have at least one plasma concentration data value after dosing.		

Population	Description
	This population will be used to the assess the PK and the relationship between PK and the
	antiviral activity of JNJ-64281802.

DENV = dengue virus; HHC = household contact; ICF = informed consent/assent form; PCR = polymerase chain reaction; PK = pharmacokinetic(s).

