4. POPULATIONS (ANALYSIS SETS) FOR ANALYSIS

For purposes of analysis, the following populations are defined:

Population	Description				
Enrolled	All participants (index cases and HHCs) who sign the ICF.				
Index Case	All participants enrolled as an index case, with a laboratory-confirmed DENV infection.				
population					
	Test results of a NS1 rapid test and/or RT-PCR test that were performed outside the study by				
	local standard-of care ≤72 hours of screening may be used to confirm the DENV infection.				
Randomized	All participants (HHCs) who are randomized in the study.				
Safety	All randomized participants who received at least one dose of study intervention.				
	This population will be used for the safety analysis.				
Primary study	All randomized participants who received at least one dose of study intervention, who had no				
population	evidence of current DENV infection at baseline (based on target not detected (TND) results for				
	DENV RNA assay and, if available, a negative/borderline result for NS1 protein assays) and				
	with at least 1 result for DENV RNA or NS1 protein assay available post baseline up to and				
	including the last day of dosing + 1 day				
	This population will be used for the primary, secondary, and exploratory efficacy analyses.				
Secondary study	All randomized participants who received at least one dose of study intervention, who had				
population	evidence of current DENV infection (based on positive results for DENV RNA or NS1 protein				
	assays at baseline) but without DENV signs and symptoms at baseline.				
	This population will be used to evaluate the exploratory objective of an antiviral effect of JNJ-				
	64281802 as early treatment.				
Complete study population	All participants included in the primary or secondary study population.				
1 1	This population will be used to investigate the key secondary endpoint of the effect of				
	JNJ-64281802 on the prevention of symptomatic DENV infection.				
PK	All participants who received at least one dose of study intervention and who have at least one				
	plasma concentration data value after dosing.				
	This population will be used to the assess the plasma concentrations of JNJ-64281802.				

 $CONFIDENTIAL-FOIA\ Exemptions\ Apply\ in\ U.S.$

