5.5.1.3. Quantitative DENV RNA VL Levels

Descriptive analyses will be done to evaluate

- the prophylactic effect of JNJ-64281802 with respect to reduction of DENV RNA among enrolled HHC who have no evidence of current DENV infection at baseline and who are infected post baseline
- the antiviral effect of JNJ 64281802 as early treatment among HHC who have evidence of DENV infection at baseline.

Data Handling Rules

Serum DENV RT-qPCR levels will be assessed using a validated quantitative DENV RT - qPCR assay.

Measurements collected from screening visit to the end of study below the lower limit of detection (LOD) and below/above the lower/upper limit of quantification (LLOQ/ULOQ) for each of the 4 serotypes on this assay will be handled according to the rules summarized in Table 5.

Table 5: Data Handling Rules for DENV RT-qPCR levels (copies/mL)

				Imputed Values		
				target not	<lloq target<="" th="">	</lloq>	
Serotype	LOD	LLOQ	ULOQ	detected ⁽¹⁾	detected ⁽²⁾	>ULOQ ⁽³⁾
DENV-1	29	1000	1 000 000 000	15	500	1 100 000 000
DENV-2	60	1000	1 000 000 000	15	500	1 100 000 000
DENV-3	36	1000	1 000 000 000	15	500	1 100 000 000
DENV-4	55	1000	1 000 000 000	15	500	1 100 000 000

⁽¹⁾ LOD (from DENV-1)/2 rounded to the nearest integer

Before any other rule is applied, the value for each day is defined as the maximum value of assessments performed on that day for each assay (DENV-1, DENV-2, DENV-3 and DENV-4). This is applied for each day separately.

Endpoint Definitions

Measurement	Formula/Definition	
Reduction of DENV RNA among HHC who have no evidence of current DENV infection at baseline and who are infected post baseline		
Peak of detectable DENV RNA	Maximum of all measured DENV RNA values	
	as early treatment among HHC who have evidence of	
current DENV infection at baseline		
Peak of post baseline detectable DENV RNA	Maximum of all post-baseline measured DENV RNA values	
Time to end of detectable DENV RNA	Minimum of (days with undetectable DENV RNA after the last detectable DENV RNA result) – Day 1 + 1	
	If the last measured DENV RNA result is still detectable, the value will be censored at the last available sample.	

⁽²⁾ LLOQ/2

⁽³⁾ ULOQ+(ULOQ/10)

Analysis Methods

Reduction of DENV RNA among HHC who have no evidence of current DENV infection at baseline and who are infected post baseline:

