5.5.1.4. DENV-associated signs and symptoms

To evaluate the antiviral effect of JNJ-64281802 as early treatment among HHC who have evidence of DENV infection at baseline, descriptive analyses will be done on the DENV-associated signs and symptoms.

DENV-associated signs and symptoms are defined as the reported solicited adverse events (Table 3). Tabulations will be provided showing the proportion of subjects per reported adverse events.

Time to end of end of DENV Infection-associated AEs will be defined as the time between the minimum of all start dates and the maximum of all end dates+1 day and will be censored if there are still signs & symptoms present at Day 28. Time to end of end of DENV Infection-associated AEs will be analyzed using Kaplan-Meier (KM) estimates. A summary table including number of participants included in the analysis, number of participants censored, 25th and 75th percentiles, and median time-to-event, with 95% CIs based on log-log transformation method, will be presented. The data will be presented graphically using the Kaplan-Meier estimate of the survival function by study drug.

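### SAP 1.1 lets the unblinded primary and secondary results decide whether two descriptive exploratory analyses are run, while SAP 4 and 5.5 commit to them and Appendix 2 records no such condition

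*SAP*

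**What the plan says.** SAP 1.1 divides the exploratory objectives into two tables. The first lists those the SAP covers. The second is introduced by "The statistical analysis for the following exploratory objectives might be performed, but will depend on the unblinded results of the primary and secondary endpoints", followed by "for hypothesis generating purposes". It holds two objectives:

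- viral-load reduction in contacts negative at baseline and infected later, with endpoint "The maximum DENV RNA levels between baseline and the last day of dosing + 1 day";
- early treatment: "To evaluate the antiviral effect of JNJ-64281802 as early treatment among HHCs who have evidence of DENV infection at baseline", with RNA and symptom endpoints.

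No rule says which result, in which direction, leads to the analyses being run, or who decides.

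Elsewhere the SAP carries no condition. Section 5.5.1.3 opens with "Descriptive analyses will be done to evaluate" and lists both RNA objectives. Section 5.5.1.4 says that "descriptive analyses will be done on the DENV-associated signs and symptoms" to address early treatment. Section 4 gives the secondary study population one stated purpose: "This population will be used to evaluate the exploratory objective of an antiviral effect of JNJ"-64281802 as early treatment. Protocol 9.3 says the same ("This population will be used to evaluate the exploratory objective of an antiviral effect of" the drug), and Protocol 3 lists both objectives without condition.

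SAP Appendix 2 explains that some exploratory analyses were left out because of early termination and lists three: infection by RNA alone, infection by NS1 alone, and symptomatic infection to Days 40, 50 and 90. The two objectives at issue are not among them.

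**The concern.** When the decision to run an analysis depends on the unblinded main results, what gets reported is a selected set. A reader who later sees the early-treatment or peak-RNA tables cannot tell whether they appear because the main result was favourable, because it was unfavourable and support was wanted elsewhere, or for another reason. If the tables are absent, the reader cannot tell why either.

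Two features make this more than a formality. First, peak RNA is measured in the same infected participants whose distribution across arms decides the primary result, so the two are not independent. Second, early treatment is the only efficacy analysis devoted to contacts infected at baseline. They otherwise contribute to efficacy only through the complete study population in the key secondary analysis, and SAP 5.4.1.2 tests that endpoint only if the high dose succeeds on the primary. If the high dose fails and the optional analysis is not run, this group has no efficacy summary of its own.

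What is at stake is the reading of exploratory evidence that may shape a later trial, not the error rate of this one.

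**Working it through.** The point rests on text, so the statements are set side by side.

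| Place | Peak RNA, infected after baseline | Early treatment, infected at baseline |
|---|---|---|
| Protocol 3 | listed, no condition | listed, no condition |
| Protocol 9.3 | – | secondary population committed to it |
| SAP 1.1 | optional, depends on unblinded results | optional, depends on unblinded results |
| SAP 4 | – | secondary population committed to it |
| SAP 5.5.1.3 | to be done | to be done (RNA) |
| SAP 5.5.1.4 | – | to be done (signs and symptoms) |
| SAP Appendix 2 | not listed as dropped or conditional | not listed as dropped or conditional |

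**Step 1: can the statements stand together?** Not as written. A programmer following 5.5 produces the tables; one following 1.1 waits for the unblinded results. Only 1.1 addresses whether the analyses are run at all, so the commitment in 5.5 does not cancel it.

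**Step 2: is the condition tied to treatment results?** Yes, in the SAP's own words. Compare the three omissions in Appendix 2, whose stated reasons compare no arms: every confirmed infection had detectable RNA, only a minority had detectable NS1, and symptomatic cases after the last dose were isolated. The SAP therefore shows that analyses can be pruned without looking at treatment differences.

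**Step 3: what do the analyses contain?** Sections 5.5.1.3 and 5.5.1.4 specify summary statistics, tabulations and Kaplan-Meier estimates with 95% intervals. There is no hypothesis test and no significance level.

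**Step 4: can the selection be sized?** Two inputs are needed.

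- *The trigger.* It is not stated. To show how much this matters, assume the trigger is the high dose meeting the 20% one-sided criterion with the 21 infections at the stop (SAP 1), using an exact conditional test with 1:1:1 allocation and no region adjustment. Given n infections in the high-dose and placebo arms, the high-dose count is Binomial(n, p), where p = (1 − PE_H)/(2 − PE_H). This is averaged over n ~ Binomial(21, q), where q = (2 − PE_H)/(3 − PE_H − PE_L).
  - Neither dose works: p = 0.5, q = 2/3, probability of running the analyses 0.13.
  - PE_H = 75%: p = 0.25/1.25 = 0.20. With PE_L = 0%, q = 1.25/2.25 = 0.556, probability 0.86. With PE_L = 75%, q = 1.25/1.50 = 0.833, probability 0.95.
  - Under the opposite trigger (run only if the high dose fails), these become 0.87, 0.14 and 0.05.

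  The SAP supports neither trigger over the other, so even the direction of selection is undetermined.
- *The number affected.* Peak RNA concerns the 21 infections at the stop, on average 21/3 = 7 per arm. The actual size of the secondary study population is not given.

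A small related gap: the protocol's early-treatment endpoint of time to end of detectable NS1 is missing from SAP 1.1, and Appendix 2 does not name it among the omissions.

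**The case against.** The best defence is that SAP 1.1 is candid. It separates core from optional analyses, says the choice depends on the data, and labels the optional ones as hypothesis generating. Section 5.5 then fixes definitions, imputation and censoring in advance, which limits analyst discretion if the analyses are run. On this view the only defect is a missing qualifier in 5.5.1.3 and 5.5.1.4. After early termination, trimming exploratory work is also reasonable.

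Much of this stands. The label is appropriate, the methods are specified in advance, and dropping sparse analyses is legitimate. Contacts infected at baseline are not otherwise ignored: they appear in the disposition, exposure and demographic summaries and in the key secondary model.

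It does not answer the central point. Adding a qualifier to 5.5 would make the text consistent but leave the decision dependent on the unblinded results. Specifying how an analysis is done does not remove selection in whether it is done, and a hypothesis drawn from a selectively run analysis is still a selected one.

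Two stronger readings are tempting and are not supported. One is that the tables would be withheld in at least 80% of trials of an ineffective drug. That follows only if success at the 20% level is the trigger, which the SAP never says. The other is that 250 to 370 participants are affected. That is the 20% planning assumption applied to planned recruitment (0.20 × 1,250 = 250; 0.20 × 1,850 = 370), whereas the study stopped at 21 of 36 target infections.

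**Conclusion.** The point holds in a limited form. SAP 1.1 makes two protocol-listed exploratory objectives depend on unblinded results without a stated trigger. SAP 4, 5.5.1.3 and 5.5.1.4 say otherwise, and Appendix 2 is silent. Whether the analyses are run can therefore follow the answer. That this carries over to reporting is an inference, though a short one: an analysis not done cannot be reported.

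The effect has no computable size. The probabilities under assumed triggers illustrate possible dependence and do not measure this plan.

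A reader might also infer that the main conclusions are compromised, or that the sponsor means to report selectively. The documents support neither. The analyses are descriptive and carry no alpha, so the primary and key secondary tests are unaffected, and the text shows a permission, not an intention. This is a worthwhile, inexpensive correction and no threat to the trial's main inference.

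**What to change.** Delete the result-dependent condition in SAP 1.1, move both objectives into the main exploratory table, and run the descriptive analyses in 5.5.1.3 and 5.5.1.4 whatever the primary result.

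If sparse data is the reason for the condition, replace it with one that does not rest on comparing arms, such as a minimum number of evaluable participants. The SAP already uses a rule of this kind, at least 6 cases, for subgroups (5.3.4) and serotypes (5.5.1.2). A count over all three arms together could be checked before unblinding. Dropping either analysis outright for a stated reason unrelated to treatment differences would also remove the selection.

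Whichever route is taken, record it in Appendix 2, and state there what became of the early-treatment NS1 endpoint.

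The cost is a few lines of SAP text, some programming of outputs whose methods are already written, and possibly sparse tables.
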